5.4.2.2. Multiple Testing Procedure

A multiple testing procedure is planned to control the overall Type 1 error rate in the study at the 2-sided 0.05 significance level. The planned procedure is depicted in Figure 2. It follows a fixed sequence approach, where the primary endpoint and the Week 12 secondary endpoints (with the exception of histologic-endoscopic mucosal improvement) for the combined guselkumab groups vs. placebo are tested prior to the secondary endpoints at Week 24. For the Week 24 endpoints, the testing sequence continues with testing all four endpoints in the guselkumab [CC] [Queen q4w [Weeks 0, 4, and 8] followed by guselkumab 200 mg SC q4w group against placebo and then testing all four endpoints in the guselkumab [Queen q4w [Weeks 0, 4, and 8] followed by guselkumab 100 mg SC q8w group against placebo. Histologic-endoscopic mucosal improvement at Week 12 is the last element of the testing sequence and is tested for the combined guselkumab groups against placebo.

[figure not shown]

Figure 2: Multiple Testing Procedure for Primary and Secondary Endpoints

Note: All p-values are two-sided

5.4.2.3. Estimator (Analysis) for the Supplementary Estimands of the Secondary Endpoints

The same estimators used for the main estimands for the secondary endpoints will be used for the supplemental estimands.

5.4.2.4. Subgroup Analyses

To evaluate the consistency of the secondary endpoints analyses, subgroup analyses for subgroups defined by the stratification variables (ADT-IR yes/no, baseline endoscopic subscore moderate [2]/severe [3]) will be performed using the FAS. The adjusted treatment difference of the combined guselkumab SC group vs. the placebo SC group and the associated p-values and 95%

confidence intervals will be provided. The treatment differences, p-values and confidence intervals will be obtained based on the common risk difference (using Mantel-Haenszel stratum weights and the Sato variance estimator), stratified by the remaining stratification factor.

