2. STATISTICAL HYPOTHESES

Primary hypothesis

The primary hypothesis of this study is that guselkumab SC induction is superior to placebo SC in achieving clinical remission at Week 12 among participants with moderately to severely active UC.

Secondary hypotheses

The secondary hypotheses of this study are listed below:

- Guselkumab SC is superior to placebo SC in achieving symptomatic remission at Week 12
- Guselkumab SC is superior to placebo SC in achieving endoscopic improvement at Week 12
- Guselkumab SC is superior to placebo SC in achieving clinical response at Week 12
- Guselkumab SC is superior to placebo SC in achieving clinical remission at Week 24
- Guselkumab SC is superior to placebo SC in achieving symptomatic improvement at Week 24
- Guselkumab SC is superior to placebo SC in achieving endoscopic improvement at Week 24
- Guselkumab SC is superior to placebo SC in achieving clinical response at Week 24
- Guselkumab SC is superior to placebo SC in achieving histologic-endoscopic mucosal improvement at Week 12

Guselkumab groups as described in Section 1.2 will be pooled for testing of all primary and secondary hypotheses at Week 12, as they received the same induction dose regimen up to Week 12. For Week 24 secondary hypotheses, each guselkumab group will be tested separately against placebo.

All Week 48 endpoints are considered exploratory.

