3. SAMPLE SIZE DETERMINATION

Sample size was determined by the power to detect significant differences in the primary endpoint of clinical remission at Week 12, and by the objective of maintaining at least 85% power across secondary endpoints at Week 12 between the combined guselkumab SC induction groups and the placebo SC group as well as for symptomatic remission at Week 24 between each guselkumab group and the placebo group, using 2-sided χ^2 tests with significance level 0.05. Combination of guselkumab SC induction groups for the primary endpoint and other Week 12 endpoints is warranted by the fact their treatment is identical through the induction period, and only differs after assessment of the primary endpoint at Week 12.

With assumed clinical remission rates of 8% for placebo and 22% for the combined guselkumab groups (based on data from Phase 2b guselkumab UC IV induction study [CNTO1959UCO3001] and Phase 3 ustekinumab UC program [CNTO1275UCO3001]), a total of 399 participants (randomized 1:1:1 for guselkumab CC q4w [Weeks 0, 4, and 8] followed by guselkumab 200 mg SC q4w: guselkumab q4w [Weeks 0, 4, and 8] followed by guselkumab 100

mg SC q8w: Placebo, yielding a 2:1 guselkumab:placebo randomization ratio for Week 12 comparisons) will ensure >95% power for the primary endpoint. This sample size also protects against a slightly lower remission rate of 20% for the combined guselkumab groups or a slightly higher remission rate of 9.5% in the placebo group (as observed in CNTO1959UCO3001), yielding a power of 90% in both cases.

Individual power values (ie, without consideration of an adjustment for multiplicity) achieved for secondary endpoints at Week 12 with a total of 399 participants (2:1 guselkumab:placebo) are described in Table 2.

Table 2: Power for Secondary Endpoints at Week 12

Endpoints	Proportion achieving endpoint in Placebo group	Proportion achieving endpoint in combined Guselkumab group	Power
Symptomatic remission	20%	45%	>99%
Endoscopic improvement	13%	28%	94%
Clinical response	30%	60%	>99%
Histologic-endoscopic mucosal improvement	8%	19%	85%
Assumed rates were based on data from the Phase 2b guselkumab UC IV induction study and the Phase 3 ustekinumab UC program			

For the secondary endpoints at Week 24, power is determined by the pairwise comparison of individual guselkumab groups to placebo (see Table 3).

Table 3: Power for Secondary Endpoints at Week 24 with a Total of 399 Participants (133 per Treatment Group)

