All data collected at unscheduled visits will not be used in "by visit" tabulation or graphs for safety analyses but will be included for analyses based on all post-baseline assessments, such as safety narratives and summary of maximum increase/decrease from Baseline for laboratory data. Unscheduled visits for efficacy assessments will be slotted to scheduled visits (see Section 5.1.1). All data collected at scheduled and unscheduled visits will be included in listings.

Combined guselkumab groups

Both guselkumab groups will receive identical study intervention for Week 0, 4, and 8. For analyses of timepoints up to Week 12, these groups will therefore be combined, and the combined group will be referred to as combined guselkumab. Note that for analyses of courses over time which include a period beyond Week 12, the two guselkumab groups may be analyzed separately.

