- **ii) Population**: Participants with moderately to severely active ulcerative colitis as defined by the inclusion/exclusion criteria.
- **iii)** Variable (Endpoint): The variable attributes for secondary endpoints at Week 24 are given in Table 8 below

Table 8: Intercurrent Events and Respective Analysis Strategies for Week 24

Endpoint	Variable attribute
Clinical	A binary response variable (response/nonresponse) where response is defined as achieving a
remission at	stool frequency subscore of 0 or 1 and not increased from baseline, a rectal bleeding subscore
Week 24	of 0, and an endoscopy subscore of 0 or 1 with no friability present on the endoscopy at Week
	24, where none of the ICEs in categories 1 to 4 and 6 outlined in Table 6 has occurred prior to
	the Week 24 visit.
Symptomatic	A binary response variable (response/nonresponse) where response is defined as achieving a
remission at	stool frequency subscore of 0 or 1 and not increased from baseline, and a rectal bleeding
Week 24	subscore of 0 at Week 24, and none of the ICEs in categories 1 to 4 and 6 outlined in Table 6
	has occurred prior to the Week 24 visit.
	•
Endoscopic	A binary response variable (response/nonresponse) where response is defined as achieving an
improvement at	endoscopy subscore of 0 or 1 with no friability present on the endoscopy at Week 24, where
Week 24	none of the ICEs in categories 1 to 4 and 6 outlined in Table 6 has occurred prior to the Week
	24 visit.
Clinical response	A binary response variable (response/nonresponse) where response is defined as achieving a
at Week 24	decrease from induction baseline in the modified Mayo score by $\geq 30\%$ and ≥ 2 points, with
at 1100K 2-1	either a ≥ 1 -point decrease from baseline in the rectal bleeding subscore or a rectal bleeding
	subscore of 0 or 1 at Week 24, where none of the ICEs in categories 1 to 4 and 6 outlined in
	Table 6 has occurred prior to the Week 24 visit
Ĭ	

- iv) Intercurrent Events and Corresponding Strategies: ICEs and the corresponding analysis strategies are defined in Table 6.
- v) Population-level summary: Difference in proportions of participants who achieved the binary response at Week 24 as defined in the variable attribute above between each of the guselkumab groups and the placebo group.

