Summaries of the proportion of participants achieving each secondary endpoint by treatment group along with the adjusted treatment difference between the combined guselkumab SC induction group (Week 12 endpoints) / individual guselkumab SC induction groups (Week 24 endpoints) and the placebo group, as well as the associated 95% confidence interval will be presented for each secondary endpoint. Each comparison against placebo will be performed in terms of the common (overall) risk difference for multiway 2x2 tables at a two-sided significance level of 0.05. Specifically, the adjusted treatment differences, 95% confidence intervals, and p-values will be in terms of the common risk difference by use of Mantel-Haenszel stratum weights and the Sato variance estimator; stratification is by ADT-IR status (Yes/No), and Mayo endoscopy subscore at baseline (moderate [2] or severe [3]).

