5.5.1. Exploratory Clinical Endpoints

5.5.1.1. Mayo Score Based Endpoints

In addition to the primary endpoint analysis described in Section 5.3.1, clinical remission with definitions given in Table 10 will be analyzed at Week 12, Week 24 and Week 48.

Table 10: Clinical Remission Definitions for Week 12, Week 24 and Week 48

Identifier	Definition
Main definition (Week 24 and Week 48 only)	Stool frequency subscore of 0 or 1 and not increased
	from baseline, a rectal bleeding subscore of 0, and an
	endoscopy subscore of 0 or 1 with no friability present
	on the endoscopy (as given in Section 5.3.1)
Legacy definition	Defined as a full Mayo score ≤2 points, with no
	individual subscore >1 point
Alternative definition	Stool frequency subscore of 0, a rectal bleeding
	subscore of 0, and an endoscopy subscore of 0 or 1
	with no friability present on the endoscopy

In addition to clinical response analyses described in Section 5.4.1.1, analyses according to definitions in Table 11 will be performed for Week 12, Week 24 and Week 48.

Table 11: Clinical Response Definitions for Week 12, Week 24 and Week 48

Identifier	Definition
Main definition (Week 24 and Week 48 only)	Decrease from baseline in the modified Mayo score by
	\geq 30% and \geq 2 points, with either a \geq 1-point decrease
	from baseline in the rectal bleeding subscore or a rectal
	bleeding subscore of 0 or 1 (as given
	in Section 5.4.1.1)
Legacy definition	Decrease from baseline in the full Mayo score by
	\geq 30% and \geq 3 points, with either a \geq 1-point decrease
	from baseline in the rectal bleeding subscore or a rectal
	bleeding subscore of 0 or 1

Symptomatic remission as defined in Section 5.4.1.1 will be evaluated at all visits, overall and by ADT-IR stratification factor. In addition, the following clinical endpoints will be evaluated:

- Deep symptomatic remission (stool frequency subscore of 0 and rectal bleeding subscore of 0) over time
- Change from baseline in absolute stool number at each visit through Week 24.
- Mayo stool frequency subscore of 0 or 1 over time

- Mayo rectal bleeding subscore of 0 over time
- Time to symptomatic remission: Time from randomization to the date of first time meeting symptomatic remission definition through Week 24 / Week 48

In addition to evaluations done at individual timepoints, the following evaluations combining timepoints will be performed (all analyses based on primary/main definitions):

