5.5.4. Analysis Methods

Unless otherwise specified, the exploratory endpoints listed and defined in Sections 5.5.1 to 5.5.3 will be analyzed based on the FAS according to the randomized intervention group, regardless of the intervention actually received.

No confirmatory tests will be performed on exploratory endpoints, regardless of the significance for primary and secondary endpoints. Nominal p-values will be presented without adjustments for multiple comparisons.

Descriptive statistics (mean, median, SD, IQ range, minimum, and maximum) will be used to summarize continuous variables. Counts and percentages will be used to summarize categorical variables. Graphical data displays (e.g., line plots) may also be used to summarize the data.

Binary endpoints

The main estimand approach and the estimator used for the secondary endpoints (Section 5.4.1.2) will be used to summarize and compare binary endpoints. Intercurrent events will be handled as specified in Table 6.

The handling of ICEs specified in Section 5.4.1.2 will be applied to each of the above binary endpoints. Participants with ICEs in categories 1-4 and 6 will be considered not to have achieved the binary endpoint, while observed values will be used for participants experiencing an ICE in category 5.

Participants with any missing data for an endpoint after application of ICE handling rules will be imputed as not having achieved the associated binary endpoint. Binary endpoints will be summarized with the number and percentage of participants who achieve the endpoint by intervention group. To compare the proportion of participants achieving the endpoints, MH tests stratified by the ADT-IR status (Yes/No), and Mayo endoscopy subscore at baseline (moderate [2] or severe [3]) will be provided. In case of rare events, Fisher's exact test will be used for intervention comparisons.

Continuous endpoints

For continuous endpoints, handling rules for ICEs as defined in Table 6:

- Composite strategy (categories 1-4 and 6): Baseline values will be assigned from the point of ICE onward
- Treatment policy strategy (category 5): Observed values will be used, if available

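### SAP 5.4.2.4 gives only a pooled guselkumab contrast for secondary-endpoint subgroups, which matches none of the per-regimen Week 24 estimands

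*SAP*

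**What the plan says.** SAP 5.4.2.4 aims to show that the secondary endpoint results are consistent across ADT-IR status and baseline endoscopy subscore. It names a single contrast, "The adjusted treatment difference of the combined guselkumab SC group vs. the placebo SC group", with a common risk difference stratified by the remaining factor. SAP 5.4.1.1 lists eight secondary endpoints. Four are at Week 24: clinical remission, symptomatic remission, endoscopic improvement and clinical response.

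Elsewhere the SAP separates the regimens at Week 24:
- Section 2, hypotheses: "For Week 24 secondary hypotheses, each guselkumab group will be tested separately against placebo".
- Section 3, Table 3: power is for one guselkumab group against placebo, 133 per group.
- Section 5.4.1.2, estimand: the difference is "between each of the guselkumab groups and the placebo group".
- Section 5.4.2.1, estimator: combined for Week 12, but "individual guselkumab SC induction groups (Week 24 endpoints) and the placebo group" for Week 24.
- Section 5.4.2.2, testing order: all four Week 24 endpoints for the 200 mg q4w regimen, then all four for 100 mg q8w.

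The reason given for pooling is limited in time. Section 3 pools because "their treatment is identical through the induction period, and only differs after assessment of the primary endpoint at Week 12". Section 5.1 says "For analyses of timepoints up to Week 12, these groups will therefore be combined".

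**The concern.** A subgroup analysis meant to show consistency has to estimate, within each stratum, the effect that was estimated overall. At Week 24 there are two such effects, one per regimen. Their average is neither of them. By then the arms differ in maintenance dosing, and Protocol 4.3 describes the two regimens as spanning roughly a four-fold range of exposure.

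If 5.4.2.4 is programmed as written, one regimen could do poorly in a stratum, for example ADT-IR participants at Week 24, and the planned table could still look reassuring because the other regimen offsets it. If the per-regimen version is added only after results are known, the choice of contrast is no longer prespecified.

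**Working it through.** **1. Basis of the plan's own Week 24 figures.** Two-sided 0.05 chi-square test for two proportions, 133 per group, rates from SAP Table 3:

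| Week 24 endpoint | Placebo vs one regimen | Stated power | Recomputed, per regimen | If pooled 2:1 |
|---|---|---|---|---|
| Clinical remission | 10% vs 27% | 95% | 95.1% | 98.8% |
| Symptomatic remission | 30% vs 60% | >99% | 99.9% | >99.9% |
| Endoscopic improvement | 13% vs 28% | 86% | 86.2% | 94.0% |
| Clinical response | 35% vs 70% | 99% | >99.9% | >99.9% |

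The clinical remission and endoscopic improvement figures reproduce per regimen and not pooled, so the Week 24 design is per regimen in its numbers as well as its text.

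**2. Search for a per-regimen subgroup contrast elsewhere.**
- Supplementary Estimands 5 and 6 (SAP 5.4.1.3) change event handling and Mayo scoring days. They do not change the contrast.
- The long subgroup list in SAP 5.7.7 is applied in 5.3.3.4 to the primary endpoint only.
- SAP 5.5.1.1 states that symptomatic remission "will be evaluated at all visits, overall and by ADT-IR stratification factor", and 5.5.4 adds: "The main estimand approach and the estimator used for the secondary endpoints (Section 5.4.1.2) will be used to summarize and compare binary endpoints". This supplies per-regimen results for symptomatic remission at Week 24 by ADT-IR, and is the only exception found.

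**3. Size of the gap.** 4 endpoints × 2 regimens × 2 factors × 2 levels = 32 contrasts. The exception supplies 1 × 2 × 1 × 2 = 4. That leaves 32 − 4 = 28: three endpoints by ADT-IR (12) and all four by baseline endoscopy subscore (16).

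**4. What pooling can hide.** The planned ADT-IR share is 40% to 50%; 45% of 133 is about 60 per arm. The half-width is 1.96·√(p₁(1−p₁)/n₁ + p₀(1−p₀)/n₀). Placebo is 10% and the regimens average 27%, both from Table 3. The gaps between regimens are assumptions, since the documents give no subgroup or regimen-specific rates.

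| Assumed regimen rates | Pooled difference (lower 95% limit) | Per-regimen differences | Weaker regimen's lower 95% limit |
|---|---|---|---|
| 27% / 27% | 17 (+6.0) | 17 / 17 | +3.4 |
| 32% / 22% | 17 (+6.0) | 22 / 12 | −0.9 |
| 37% / 17% | 17 (+6.2) | 27 / 7 | −5.2 |

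Worked example, first row:
- Per regimen: 1.96·√(0.27·0.73/60 + 0.10·0.90/60) = 13.6 points, and 17 − 13.6 = +3.4.
- Pooled, with 120 against 60: 1.96·√(0.27·0.73/120 + 0.10·0.90/60) = 11.0 points, and 17 − 11.0 = +6.0.

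**5. Precision given up by splitting.** Clinical remission half-widths, per regimen vs pooled: 14.4 vs 11.7 at 53 per arm (40%), 13.6 vs 11.0 at 60 (45%), 12.9 vs 10.5 at 66 (50%). Over all four Week 24 endpoints the increase is 2.0 to 2.7 points at 53 to 66 per arm. In the non-ADT-IR stratum, which can reach 60% (about 80 per arm), the smallest increase is about 1.9, for clinical response. No split by endoscopy subscore is given. The increase scales with 1/√n, so the same figures apply if those strata also hold 40% to 60% of participants.

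**The case against.** The best counter-argument is that SAP 5.1 defines combined guselkumab for timepoints up to Week 12, so 5.4.2.4 may be read as covering Week 12 only. On that reading no wrong Week 24 analysis is planned. But 5.4.2.4 addresses the secondary endpoints without restriction, so four of its eight endpoints would then have no contrast at all. The section is deficient on either reading, and the same correction resolves both.

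SAP 5.1 also says that the groups may, rather than must, be analyzed separately in courses over time beyond Week 12, and the SAP reports the combined group past Week 12 for adverse events, laboratory data and PK (5.6.2, 5.6.3.1, 5.7.1.1). In each of those three places the individual groups appear alongside. None supports a pooled-only efficacy contrast.

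Several points stand. The protocol commits to subgroup analyses only for the primary endpoint (9.4.2.2), so no protocol commitment is broken. The 10- and 20-point gaps are hypothetical. Under the SAP's assumption of equal regimen rates, pooling only gains precision (11.0 vs 13.6). The intervals above are unstratified Wald intervals, not the planned Mantel-Haenszel estimate with Sato variance. The count of 28 measures missing specification, not harm.

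**Conclusion.** The concern holds. The stated subgroup contrast matches the Week 12 secondary endpoints and none of the Week 24 ones, leaving 28 of 32 regimen-specific Week 24 contrasts unspecified. A pooled lower limit near +6 is compatible with a weaker-regimen lower limit anywhere from +3.4 to −5.2, given the Table 3 average rate, about 60 per arm and an assumed regimen gap of 0 to 20 points.

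The consequence is limited to interpretation of supportive results. Confirmatory testing, type I error and sample size do not change, and overall per-regimen Week 24 estimates remain available under 5.4.2.1. It should be corrected because 5.4.2.4 cannot otherwise serve its stated purpose at Week 24.

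SAP 5.5.4.1 has a related, lesser ambiguity. It repeats the combined contrast for histologic endpoints without naming timepoints, and the section it refers to (5.5.1.2) includes Week 48.

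**What to change.** In SAP 5.4.2.4, carry over the split already used in 5.4.2.1: combined guselkumab against placebo for the Week 12 endpoints, and each guselkumab group against placebo for the Week 24 endpoints, stratified by the remaining factor. Label any pooled Week 24 subgroup result as supportive and show it beside the per-regimen results.

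In SAP 5.5.4.1, state the timepoints. If Week 48 histology is included, compare each group with placebo there.

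The cost is SAP wording, extra table columns and the wider subgroup intervals shown above. No data collection changes.

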5.5. Exploratory Endpoints Analysis

The exploratory clinical endpoints, and exploratory endpoints related to Health-Related Quality of Life outcomes, inflammatory biomarkers and health economics will be analyzed. These timepoints will be summarized for each applicable timepoint through Week 48 using the FAS.

5.5.1. Exploratory Clinical Endpoints

5.5.1.1. Mayo Score Based Endpoints

In addition to the primary endpoint analysis described in Section 5.3.1, clinical remission with definitions given in Table 10 will be analyzed at Week 12, Week 24 and Week 48.

Table 10: Clinical Remission Definitions for Week 12, Week 24 and Week 48

Identifier	Definition
Main definition (Week 24 and Week 48 only)	Stool frequency subscore of 0 or 1 and not increased
	from baseline, a rectal bleeding subscore of 0, and an
	endoscopy subscore of 0 or 1 with no friability present
	on the endoscopy (as given in Section 5.3.1)
Legacy definition	Defined as a full Mayo score ≤2 points, with no
	individual subscore >1 point
Alternative definition	Stool frequency subscore of 0, a rectal bleeding
	subscore of 0, and an endoscopy subscore of 0 or 1
	with no friability present on the endoscopy

In addition to clinical response analyses described in Section 5.4.1.1, analyses according to definitions in Table 11 will be performed for Week 12, Week 24 and Week 48.

Table 11: Clinical Response Definitions for Week 12, Week 24 and Week 48

Identifier	Definition
Main definition (Week 24 and Week 48 only)	Decrease from baseline in the modified Mayo score by
	\geq 30% and \geq 2 points, with either a \geq 1-point decrease
	from baseline in the rectal bleeding subscore or a rectal
	bleeding subscore of 0 or 1 (as given
	in Section 5.4.1.1)
Legacy definition	Decrease from baseline in the full Mayo score by
	\geq 30% and \geq 3 points, with either a \geq 1-point decrease
	from baseline in the rectal bleeding subscore or a rectal
	bleeding subscore of 0 or 1

Symptomatic remission as defined in Section 5.4.1.1 will be evaluated at all visits, overall and by ADT-IR stratification factor. In addition, the following clinical endpoints will be evaluated:

- Deep symptomatic remission (stool frequency subscore of 0 and rectal bleeding subscore of 0) over time
- Change from baseline in absolute stool number at each visit through Week 24.
- Mayo stool frequency subscore of 0 or 1 over time

- Mayo rectal bleeding subscore of 0 over time
- Time to symptomatic remission: Time from randomization to the date of first time meeting symptomatic remission definition through Week 24 / Week 48

In addition to evaluations done at individual timepoints, the following evaluations combining timepoints will be performed (all analyses based on primary/main definitions):

- Sustained clinical remission: Clinical remission at Week 12 and Week 24 (Week 24 DBL) and at Week 12, Week 24 and Week 48 (Week 48 DBL)
- Maintenance of clinical remission at Week 24 and at Week 48 among participants achieving clinical remission at Week 12
- Maintenance of clinical remission through Week 48 (at both Week 24 and Week 48) among participants achieving clinical remission at Week 12
- Sustained clinical response: Clinical response at Week 12 and Week 24 (Week 24 DBL), Week 12, Week 24 and Week 48 (Week 48 DBL)
- Symptomatic remission over time among participants achieving symptomatic remission at Week 12 (Week 48 DBL only)
- Durable symptomatic remission through Week 48: Defined as achieving symptomatic remission for >80% of all visits between Week 0 (excluding) and Week 48 (including)

The changes from baseline over time will be evaluated for full Mayo score, modified Mayo score, partial Mayo score, and Mayo stool frequency and rectal bleeding and subscores. The full Mayo score and the modified Mayo scores require an endoscopy and will therefore only be evaluated at Week 12, Week 24 and Week 48. The partial Mayo score will be evaluated at all visits.

The following evaluations for completeness/missingness of the Mayo score will be done at Week 12, Week 24 and Week 48:

- Summary of completeness of modified Mayo score and the full Mayo score
- Number of participants who experienced intercurrent events prior to Week 12, prior to Week 24 and prior to Week 48
- Summary of Mayo subscores through Week 12, through Week 24, and through Week 48
- Summary of missing modified Mayo score and the full Mayo score components after accounting for ICE strategies and by intercurrent event occurrence

